6.14.2. Adverse Events

Adverse events will be classified based upon the latest version of the MedDRA. AEs will be recorded at every study visit. Condition starting on or after the date of informed consent will be considered an AE. A preexisting condition which worsens in severity on or after the date of informed consent will be considered and recorded as an AE on the *AE* eCRF page from the date of worsening onwards.

A treatment-emergent adverse event (TEAE) is defined as an event that first occurred or worsened in severity after baseline and on or prior to the date of the last visit within the defined treatment period. Both the date/time of the event and the date/time of the dose (that is, injection) are considered when determining TEAEs. A TEAE will be assigned to the study period to which it is considered treatment-emergent:

- The MedDRA lowest level term (LLT) will be used when classifying AEs as treatment-emergent.

- The maximum severity recorded for each LLT prior to the first dose date/time in the Induction Dosing Period will be used as the pre-treatment severity for that LLT. If an event during the baseline period has missing severity and the event persists during the treatment period, then it will be considered as treatment-emergent, regardless of the post-baseline level of severity. Events with a missing severity during the treatment period will be considered treatment-emergent.
- AEs with a particular LLT will be classified as treatment-emergent if they first start on or after the first dose date/time in the treatment period (i.e., a patient has no pre-existing conditions with that LLT), or if the severity is greater than the pre-treatment severity for that LLT. If a partial AE start date/time is present, the date/time will be compared as far as possible to the treatment start date/time in order to determine whether the event is treatment-emergent or not. If there is any doubt, the event will be flagged as treatment-emergent.

A follow-up emergent adverse event (FEAE) is defined as an event that first occurred or worsened in severity after the date of Visit 12 (that is, Week 24) or the ETV:

- The MedDRA LLT will be used when classifying AEs as follow-up emergent.
- For AEs that are ongoing at the date of Visit 12 or ETV, the maximum severity recorded for each LLT on or prior to the date of Visit 12 or ETV will be used as the follow-up baseline severity for that LLT.
- If a partial AE start date is present, the date will be compared as far as possible to the date of Visit 12 or ETV in order to determine whether the event is follow-up emergent or not. If there is any doubt, the event will be flagged as follow-up emergent, unless the same event was already counted as treatment-emergent during the Blinded Treatment Periods.

AEs and TEAEs will be summarized and analyzed for the safety population for the Blinded Treatment Periods.

- An overall summary of AEs including the number and percentage of patients who experienced TEAE, TEAE by maximum severity, death, serious adverse events (SAE), TEAE related to study treatment, discontinuations from the treatment due to an AE, and TEAEs of special interest.
- TEAE by system organ class (SOC) and preferred term (PT).
- TEAE by PT.
- TEAE by maximum severity, SOC and PT.

FEAEs will be summarized for the post-treatment follow-up population for the Post-Treatment Follow-Up Period:

- FEAE by PT.

If a partial or completely missing AE start date/time or end date/time is present the following imputation rules will be utilized in the analysis:

- For the start date:
 - If year, month, and day are missing, then use the earlier of the patient's first visit date or the consent date.
 - If either month or month and day are missing, then use January 1.
 - If only day is missing, impute the first day of the month.
- For the start time:
 - Impute as 23:59
- For the end date:
 - If year, month, and day are missing, then use the patient's last visit date in the follow-up period.
 - If either month or month and day are missing, then use December 31.
 - If only day is missing, then use the last day of the month.
 - The imputed date will not be beyond the patient's last visit date in the follow-up period.
- For the end time:
 - Impute as 23:59.
- If there is any doubt, the event will be flagged as treatment-emergent or follow-up emergent according the corresponding study period. If a follow-up emergent event was already counted as treatment-emergent during the prior treatment period, it will not be counted as a follow-up emergent event.

In general, for all AE related summaries, the number and percentage of patients experiencing the events will be presented by treatment. The events will be ordered by decreasing frequency in the overall group, followed in the order of ixekizumab and then in the order of guselkumab treatment, within SOC and/or PT for sorting.

A by-patient listing of all AEs will be provided.

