	
The Injection Site Reaction eCRF page captures the injection site reactions identified by the investigator. These TEAEs will be summarized within the MedDRA HLT by maximum severity or category. If more than one TEAE of injection site reaction occurs, the event with the worst value (within the individual categories: redness, swelling and pain) will be used.
 
Redness (Scored 0-4)
 
 ○ [0] Subject’s normal skin color, no increased redness ○ [1] Noticeable, but very mild redness ○ [2] Clearly red ○ [3] Bright red ○ [4] Dark with some scar formation 
Swelling (Scored 0-4 after running a finger over injected area)
 
 ○ [0] No bump ○ [1] Barely noticeable ○ [2] Clear bump but very thin ○ [3] Clear bump 1 mm thick ○ [4] Clear bump 2 mm thick or more 
Pain (including burning) (Scored 0-3)
 
 ○ [0] None ○ [1] Mild ○ [2] Moderate ○ [3] Severe 
The duration of TEAE PT for Injection Site Reactions is defined as: Duration of TEAE PT for ISRs (in weeks) = (End date of AE – Start date of AE + 1) / 7.
 
Patients who do not have the PT will not be included in the analysis. If the TEAE has not been reported as ended by the date of completion from the study, or date of early discontinuation, it will be censored as of that date. If a patient has multiple episodes of the same TEAE, the episode with the greatest severity will be used for the duration of event calculation. If a patient has multiple episodes of the same TEAE with the same severity, the episode with the longest duration will be used for the duration of event calculation.
 
The number of TEAE PT for ISRs per 100 active injections is defined as: Number of TEAE PT for ISRs per 100 active injections = $100 \times \text{total number of AEs} / \text{total active injections}.$
	
ISRs by PT within HLT, Number of treatment-emergent ISRs per 100 active injections by PT within HLT
 
Time to onset of initial treatment-emergent ISRs by PT within HLT

--	--	---

	
Time to onset of initial TEAE PT for ISRs is defined as: Time to onset of initial TEAE PT for ISRs (in days) = Start date of first AE – first injection date + 1.
	

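### Imputed adverse-event start dates have no lower bound at the first injection, so events whose partial date spans that injection can be treatment-emergent by flag but pre-dose by date

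*SAP*

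**What the plan says.** SAP 6.14.2 sets the treatment-emergent flag and the imputed date by separate rules.

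- **Flag.** "If a partial AE start date/time is present, the date/time will be compared as far as possible to the treatment start date/time". Where that does not settle the matter, "If there is any doubt, the event will be flagged as treatment-emergent".
- **Imputed start date.** Day missing: "If only day is missing, impute the first day of the month". Month missing, with or without the day: "If either month or month and day are missing, then use January 1". Nothing known: "If year, month, and day are missing, then use the earlier of the patient's first visit date or the consent date".
- **Imputed start time.** "Impute as 23:59". This changes the clock time, not the date.
- **Bound.** For end dates only: "The imputed date will not be beyond the patient's last visit date in the follow-up period". No matching limit is given for start dates.

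Table RHCR.6.8 in SAP 6.14.3.1 then uses the start date. Time to onset of the initial injection-site reaction, in days, is "Start date of first AE – first injection date + 1". Duration in weeks, for injection-site reactions and for infections, is end date minus start date plus one, divided by seven. Neither entry excludes or truncates imputed starts.

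**The concern.** The flag resolves doubt towards after dosing, while the imputation resolves it towards the earliest date. Where the missing part of the date covers the first injection, one event is then treatment-emergent in one table and dated before treatment in another. For an injection-site reaction that is impossible.

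Injection-site reactions and infections are both adverse events of special interest in Protocol 9.2.1.2. Protocol 10.3.1 summarises continuous data with the minimum and maximum, so a single such record would show as an impossible minimum time to onset.

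Two selection rules in Table RHCR.6.8 can also favour the bad value within a patient. Time to onset takes the first event, so a reaction imputed to a pre-dose date can displace a fully dated one. Among episodes of equal severity, the longest duration is the one used.

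**Working it through.** The plan states no figure on this point to reproduce. The check applies the SAP's rules to dates.

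**Inputs.** Start-date and flag rules: SAP 6.14.2. Onset and duration formulas: SAP Table RHCR.6.8. Screening visit 5 to 28 days before Week 0: Protocol 5.1.1 and Schedule of Activities. Assumptions: consent is on the Visit 1 date, and first-injection dates are spread evenly over a 365-day year.

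**When the fault arises.** A date with only the day missing must name the month of the first injection. A date with the month missing must name its year. A completely missing date always qualifies.

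**Example, first injection 15 May (non-leap year).** Time to onset = start - first injection + 1.

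| Recorded onset | Imputed start | Time to onset | True value if treatment-emergent | Error |
|---|---|---|---|---|
| May, no day | 1 May | -14 + 1 = -13 | 1 to 17 (15 to 31 May) | 14 to 30 days |
| Year only | 1 January | -134 + 1 = -133 | at least 1 | at least 134 days |
| Nothing, consent 28 days earlier | consent date | -28 + 1 = -27 | at least 1 | at least 28 days |

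**General case.**

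- *Day missing.* If the first injection falls on day d of the month, time to onset is 1 - d + 1 = 2 - d. This is +1 for d = 1, 0 for d = 2 and negative from d = 3. The range is +1 to -29, the mean about -13.7, and the value is negative for 341 of 365 injection dates (93%).
- *Month missing.* The range is +1 to -363, negative for over 99% of injection dates.
- *All missing.* With Visit 1 from 5 to 28 days before dosing, the range is -5 + 1 = -4 to -28 + 1 = -27, always negative. Earlier consent makes it more negative.

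**Duration.** Pre-dose time added, compared with a start at the first injection:

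- *Day missing:* (d - 1)/7 weeks, mean 2.1, maximum 30/7 = 4.3.
- *Month missing:* mean 26 weeks, maximum 364/7 = 52.

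Worked case with first injection 20 March and event end 27 March:

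- Start at first injection: 8/7 = 1.14 weeks, onset day 1.
- Day missing: 27/7 = 3.86 weeks, onset day -18.
- Month and day missing: 86/7 = 12.29 weeks, onset day -77.

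**Aggregate size.** The documents do not say how common partial dates are. Suppose 0.5% to 2% of the records in the onset summary were of the missing-day type in the 15 May example. The mean would fall by 0.005 × 14 = 0.07 to 0.005 × 30 = 0.15 days at the low end, and by 0.02 × 14 = 0.28 to 0.02 × 30 = 0.60 days at the high end. Year-only records would move it more per record.

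**The case against.** The case for leaving the text alone is that the flag is deliberately conservative and separate from imputation, that few events can be affected, and that the SAP's main safety results do not use the imputed date. Much of this stands.

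- A reader might infer that every partially dated event gets a pre-dose onset. It does not. In a 24-week treatment period, a missing day matters only in the calendar month of the first injection; in later months the first of the month is already post-dose.
- A reader might infer that treatment-emergent events are misclassified or lost. The flag compares the recorded part of the date with treatment start and resolves doubt towards treatment-emergent, so counts and Fisher comparisons of incidence do not depend on the imputed date.
- A reader might blame all lengthened durations on the missing floor. First-of-month imputation lengthens a duration in any month; only the pre-dose part comes from the missing floor.
- Adverse events are reviewed at every visit (Weeks 0, 1, 2 and 4, then two-weekly to Week 12), and injection-site reactions have their own eCRF page. Year-only or fully missing onsets should be rare. The infection summary is limited to common terms and narrow opportunistic-infection terms.

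What does not stand is the idea that the text already prevents the problem. No floor appears elsewhere in either document. The sponsor's compound-level safety standard could not be checked, but SAP 6.14.2 sets out its date rules in full without deferring to it. The 23:59 start time helps only with onsets on the day of injection.

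**Conclusion.** The point holds as a minor error in a stated rule. When the missing part of a start date spans the first injection, the SAP as written usually produces a zero or negative time to onset for an injection-site reaction, and adds pre-dose time to durations of injection-site reactions and infections. A year-only date moved to 1 January can even precede consent, although SAP 6.14.2 counts only conditions that start or worsen from consent onwards as adverse events.

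Per affected record the error is large: 14 to 30 days for a missing day and at least 134 days for a missing month in the 15 May example. The -13 and -133 themselves are imputed values and understate the error. In aggregate the effect is probably small, but that rests on partial dates being uncommon, which the documents do not show. Treatment-emergent incidence and all efficacy analyses are unaffected.

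**What to change.** Add one sentence to the start-date rules in SAP 6.14.2: *For an event classified as treatment-emergent, an imputed start date/time earlier than the first injection is set to the date/time of the first injection, where the recorded parts of the start date and the end date allow it.* The minimum time to onset then becomes 1 day. This mirrors the bound already placed on end dates.

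The cost is a sentence and a line of code, with no new data. It is better settled before the Week 12 database lock, when Protocol 10.3.7 gives part of the study team the treatment codes, than left to an undocumented programming choice.

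There are two drawbacks. Floored events will cluster at day 1, and durations of partially dated events in later months will still be lengthened by first-of-month imputation.

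Two further changes are not needed. A matching floor at Visit 12 or the early termination visit would alter no specified summary, because the SAP plans only counts of follow-up emergent events. Excluding every event with an imputed date from the onset and duration summaries would discard real events and make the floor redundant there.

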6.14.3. Deaths, Other Serious Adverse Events, and Other Notable Adverse Events

By-patient listings of deaths, SAEs, AEs leading to discontinuation will be provided, respectively.

All deaths will be included, regardless of the investigator's or the Sponsor's judgment about causality, including:

- any deaths occurring during participation in the study in the database for which data are being presented
- any deaths occurring after a patient leaves (is discontinued from or completed) the study in the database for which data are being presented if the death is:
 - the result of a process initiated during the study, regardless of when it actually occurred, or
 - occurs during the Period 4 after discontinuation of study drug.

The following summary tables (including treatment comparison) will be provided for the safety population for the Blinded Treatment Periods:

- SAEs by SOC and PT
- AEs that lead to treatment discontinuation (including death) by SOC and PT.

Follow-up emergent serious adverse event (FESAE) is defined as an SAE that first occurred or worsened in severity after the date of Visit 12 (that is, Week 24) or the ETV. The following summary tables will be provided for the follow-up population for the Post-Treatment Follow-Up Period:

- Follow-up emergent SAEs (FESAEs) by SOC and PT
- FEAEs that lead to treatment discontinuation (including death) by SOC and PT.

6.14.3.1. Special Safety Topics including Adverse Events of Special Interest

Safety information on special topics including AEs of special interest (AESI) will be presented by treatment. [Table RHCR.6.8](#) provides the definitions/derivations and analyses methods (including analyses, summaries and by-patient listings) of special safety topics including AESIs.

Potential AESIs will be identified by a standardized MedDRA query (SMQ) or a Lilly-defined MedDRA PT listing. Preferred terms within an SMQ will be classified as broad and narrow. In the Lilly-defined MedDRA PT listings, Lilly has provided the broad and narrow classification. The Lilly-defined broad terms are for a more sensitive search of potential events of interest and the Lilly-defined narrow terms are for a more specific search. Therefore, the summaries will include the classifications of broad term (same as pooling narrow and broad terms together) and narrow term.

In the event that the listing of terms or analysis changes for a special safety topic, it will be documented in the compound level safety standard (Program Safety Analysis Plan 2018) which will supersede this document; it will not warrant an amendment to the individual study SAP.

Fisher's exact tests will be used to compare the treatment groups for the safety population during the Blinded Treatment Periods.

Table RHCR.6.8. Definitions and Analyses of Special Safety Topics including Adverse Events of Special Interest

Special Safety Topic	Definition / Derivation	Analysis / Summary / Listing
Hepatic	
Hepatic AE analysis will include events that are potentially drug-related hepatic disorders by using the Medical Dictionary for Regulatory Activities (MedDRA) PTs contained in any of the following standardized MedDRA query (SMQ) or sub-SMQ as defined in MedDRA:
 
 • Broad and narrow terms in the Liver related investigations, signs and symptoms (20000008) • Broad and narrow terms in the Cholestasis and jaundice of hepatic origin (20000009) • Broad and narrow terms in the Hepatitis, non-infectious (20000010) • Broad and narrow terms in the Hepatic failure, fibrosis and cirrhosis and other liver damage (20000013) • Narrow terms in the Liver-related coagulation and bleeding disturbances (20000015) 	
Blinded Treatment Periods (Fisher’s exact test): TEAEs by PT within SMQ or sub-SMQ

	
Elevations in hepatic laboratory tests (alanine aminotransferase [ALT], aspartate aminotransferase [AST], alkaline phosphatase [ALP], total bilirubin) using Performing Laboratory Reference Ranges are defined as:
 
 • Include scheduled visits, unscheduled visits, and repeat measurements. • ALT or AST: maximum post-baseline measurement ≥ 3 times (3\times), 5 times (5\times), 10 times (10\times), and 20 times (20\times) the Performing lab upper limit of normal (ULN) for all patients with a post-baseline value. • The analysis of 3\times ULN will contain 4 subsets: patients whose non-missing maximum baseline value is $\leq 1 \times$ ULN, $>1 \times$ ULN to $<3 \times$ ULN, $\geq 3 \times$ ULN, or missing. • The analysis of 5\times ULN will contain 5 subsets: patients whose non-missing maximum baseline value is $\leq 1 \times$ ULN, $>1 \times$ ULN to $<3 \times$ ULN, $\geq 3 \times$ ULN to $<5 \times$ ULN, $\geq 5 \times$ ULN, or missing. • The analysis of 10\times ULN will contain 6 subsets: patients whose non-missing maximum baseline value is $\leq 1 \times$ ULN, $>1 \times$ ULN to $<3 \times$ ULN, $\geq 3 \times$ ULN to $<5 \times$ ULN, $\geq 5 \times$ ULN to $<10 \times$ ULN, $\geq 10 \times$ ULN, or missing. • The analysis of 20\times ULN will contain 7 subsets: patients whose non-missing maximum baseline value is $\leq 1 \times$ ULN, $>1 \times$ ULN to $<3 \times$ ULN, $\geq 3 \times$ ULN to $<5 \times$ ULN, $\geq 5 \times$ ULN to $<10 \times$ ULN, $\geq 10 \times$ ULN to $<20 \times$ ULN, $\geq 20 \times$ ULN, or missing. • Total bilirubin: maximum post-baseline measurement ≥ 1.5 times (1.5\times) and ≥ 2 times (2\times) the Performing lab ULN for all patients with a post-baseline value 
 ○ The analysis of 1.5\times ULN will contain 4 subsets: patients whose non-missing maximum baseline value is $\leq 1 \times$ ULN, $>1 \times$ ULN to $<1.5 \times$ ULN, $\geq 1.5 \times$ ULN, or missing. ○ The analysis of 2\times ULN will contain 5 subsets: patients whose non-missing maximum baseline value is $\leq 1 \times$ ULN, $>1 \times$ ULN to $<1.5 \times$ ULN, $\geq 1.5 \times$ ULN to $<2 \times$ ULN, $\geq 2 \times$ ULN, or missing. 	
Blinded Treatment Periods (Fisher’s exact test): Elevations in hepatic laboratory tests: maximum baseline category to abnormal maximum post-baseline category
 
Post-Treatment Follow-Up Period (Summary): Elevations in hepatic laboratory tests: maximum baseline category to abnormal maximum post-baseline category


	
ULN, or missing.
 
 Alkaline phosphatase (ALP): maximum post-baseline measurement >1.5 times (1.5×) the Performing lab ULN for all patients with a post-baseline value, and divided into 4 subsets: patients whose non-missing maximum baseline value is ≤1× ULN, >1× ULN to ≤1.5× ULN, >1.5× ULN, or missing. The number and percentages of patients meeting the following elevated hepatic criteria: maximum ALT ≥ 3× ULN and maximum Total Bilirubin ≥2× ULN during the treatment period will be summarized. 	
	
Shift for ALT, AST, and total bilirubin from maximum baseline to maximum post-baseline will be produced with the requirements using Performing Laboratory Reference Ranges:
 
 Include scheduled visits, unscheduled visits, and repeat measurements. Use the maximum non-missing value in the baseline period. Use the maximum non-missing post-baseline value within each study period. Categories are: 
 ALT: ≤1× ULN, >1 to <3× ULN, ≥3 to <5× ULN, ≥5 to <10× ULN, ≥10 to <20× ULN, and ≥20× ULN AST: ≤1× ULN, >1 to <3× ULN, ≥3 to <5× ULN, ≥5 to <10× ULN, ≥10× to <20× ULN and ≥20× ULN Total bilirubin: ≤1× ULN, >1 to <1.5× ULN, ≥1.5 to <2× ULN, ≥2× ULN ALP; ≤1× ULN, >1 to ≤1.5× ULN, >1.5× ULN With additional categories: 
 Decreased: post-baseline category < baseline category Increased: post-baseline category > baseline category Same: post-baseline category = baseline category 	
Blinded Treatment Periods (Summary): Shifts from maximum baseline to maximum post-baseline category
 
Post-Treatment Follow-Up Period (Summary): Shifts from maximum baseline to maximum post-baseline category

	
Evaluation of Drug-Induced Serious Hepatotoxicity (eDISH) plot: Each patient with at least one post-baseline ALT and total bilirubin contributes one point to the plot. The maximum ALT measurement and the maximum total bilirubin measurement after the first injection will be included. Patients will be classified into 2 groups: never on ixekizumab or ever on ixekizumab. The measurements do not need to be taken at the same blood draw. There will only be 1 eDISH plot for each indication regardless of treatment periods.
	
eDISH plot


Cytopenias
	
Cytopenias are defined using the PTs from the following 2 sub-SMQs of the Haematopoietic cytopenias SMQ (20000027) as specified in MedDRA:
 
 Broad and narrow terms in the Haematopoietic leukopenia (20000030) Broad and narrow terms in the Haematopoietic thrombocytopenia (20000031) 	
Blinded Treatment Periods (Fisher’s exact test): TEAEs by PT within sub-SMQ

Infections
	
Infections are events including all infections (defined using all the MedDRA PTs from the Infections and infestations SOC), serious infections, potential opportunistic infections (OIs), and infections resulting in anti-infective medication administration (i.e., antibacterial, antiviral, antifungal, antiparasitic treatment).
	
Blinded Treatment Periods (Fisher’s exact test): SAEs by PT, AEs leading to treatment discontinuation (including death) by PT, TEAEs by PT, TEAEs by maximum severity by PT

	
Anti-infective medications are defined in the compound level safety standard, including antibiotics, antifungals, antivirals, or antiprotozoals.
	
Listing: TEAE with anti-infective medications

	
The list of MedDRA terms used to identify infections that are pre-defined as potential OIs are found in the compound level safety standards. This list contains PTs as contained within Categories (narrow or broad) from the Infections and infestations SOC and from the Investigations SOC which can assist in identifying potential OIs. The narrow terms are considered opportunistic infections unless medical review determines that the reported term is not consistent with the patient’s clinical history/presentation/course. Medical review of broad terms is needed for final determination of patients meeting the program definition of OIs.
 
The number and percentage of patients with TEAEs that represent potential OIs and as potential OIs will be summarized by treatment group using MedDRA PT nested within categories. Events will be ordered by decreasing frequency in the ixekizumab group nested within categories.
	
Blinded Treatment Periods (Fisher’s exact test): TEAE of OIs by PT within Category
 
Listing: TEAE of OIs

	
The duration of each common ($\geq 1\%$ of total ixekizumab) TEAE PT of Infections and narrow terms for OIs is defined as: Duration of treatment-emergent AE Infections (in weeks) = $(End\ date\ of\ AE - Start\ date\ of\ AE + 1) / 7.$ Patients who do not have the PT will not be included in the analysis. If the TEAE has not been reported as ended by the date of completion from the study, or date of early discontinuation, it will be censored as of that date. If a patient has multiple episodes of the same TEAE, the episode with the greatest severity will be used for the duration of event calculation. If a patient has multiple episodes of the same TEAE with the same severity, the episode with the longest duration will be used for the duration of event calculation.
	
Blinded Treatment Periods (Summary): Duration of common TEAEs- infections and narrow terms for opportunistic infections

Allergic Reactions/Hypersensitivities
	
Allergic reactions/hypersensitivity events will be categorized as either anaphylaxis or non-anaphylaxis events (these will refer to events that are not localized to the site of injection) and summarized separately. Medical reviews are needed for final determination of patients with allergic-reactions/hypersensitivities.
	
Blinded Treatment Periods (Fisher’s exact test): TEAE by PT within Category, TEAE by maximum severity by

	
Allergic Reactions/Hypersensitivity Events, Anaphylaxis: Anaphylaxis has been broadly defined as “a serious allergic reaction that is rapid in onset and may cause death” (Sampson et al. 2006). Identification of cases of potential anaphylaxis from the clinical trial data involves two screening criteria:
 
 • designed to specifically identify cases (following Criterion 1) based on narrow terms from the MedDRA SMQ for anaphylactic reaction (20000021). Criterion 1 for anaphylaxis is defined by the presence of a TEAE based on the following MedDRA PTs from the anaphylactic reaction SMQ: 
 ○ Anaphylactic reaction ○ Anaphylactic shock ○ Anaphylactoid reaction ○ Anaphylactoid shock ○ Kounis Syndrome ○ Type I hypersensitivity • to identify possible cases, following Criterion 2 as defined by Sampson et al (2006). Criterion 2 for anaphylaxis requires having TEAEs from two or more of four categories of AEs as described by Sampson et al (2006). Occurrence of these events should be nearly coincident; based on recording of events on eCRFs. All qualifying events must be within 1 day of study drug injection. 
The 4 categories to be considered in Criterion 2 are:
 
 ○ Category A: Involvement of the skin-mucosal tissue ○ Category B: Respiratory compromise ○ Category C: Reduced blood pressure or associated symptoms ○ Category D: Persistent gastrointestinal symptoms 	
PT within Category, SAE by PT within Category, AE leading to treatment discontinuation (including death) by PT within Category,

--	--	--

	
Summaries of Criterion 2 anaphylactic TEAEs will be provided by the specific combination of categories as follows:
 
 • AB: events based on meeting Category A and Category B (but no other category) • AC: events based on meeting Category A and Category C (but no other category) • AD: events based on meeting Category A and Category D (but no other category) • BC: events based on meeting Category B and Category C (but no other category) • BD: events based on meeting Category B and Category D (but no other category) • CD: events based on meeting Category C and Category D (but no other category) • ABC: events based on meeting Category A, Category B and Category C (but no other category) • ABD: events based on meeting Category A, Category B and Category D (but no other category) • ACD: events based on meeting Category A, Category C and Category D (but no other category) • BCD: events based on meeting Category B, Category C and Category D (but no other category) • ABCD: events based on meeting each of the 4 Criterion 2 categories 
Summaries of treatment-emergent anaphylactic AEs will be provided for patients meeting each of the 2 criteria and for patients who meet either criteria overall. Severity of treatment-emergent Criterion 2 anaphylactic AEs will be based on the maximum severity of the specific events met by the patient. Maximum severity of an (or overall) treatment-emergent anaphylactic AE will be based on the maximum severity within Criterion 1 and/or Criterion 2.
 
Allergic Reactions/Hypersensitivity Events, Non-Anaphylaxis: TEAEs of allergic reaction/hypersensitivity categorized as non-anaphylaxis events are defined by the narrow terms within Hypersensitivity SMQ (20000214) excluding the PTs noted in the compound level safety standards and excluding the anaphylactic events as defined above.
	

Injection Site Reactions
	
Injection site reaction is defined using the PTs from the MedDRA HLT of Injection site reactions as specified by MedDRA excluding the following 10 PTs:
 
 1) Embolia cutis medicamentosa 2) Injection site joint discomfort 3) Injection site joint effusion 4) Injection site joint redness 5) Injection site joint infection 6) Injection site joint inflammation 7) Injection site joint movement impairment 8) Injection site joint pain 9) Injection site joint swelling 10) Injection site joint warmth. 	
Blinded Treatment Periods (Fisher’s exact test): TEAEs by PT within HLT, TEAEs by maximum severity by PT within HLT, TEAEs identified by the investigator by PT within HLT: by maximum severity, by maximum redness category, by maximum swelling category, by maximum pain category
 
Duration of treatment-emergent

	
The Injection Site Reaction eCRF page captures the injection site reactions identified by the investigator. These TEAEs will be summarized within the MedDRA HLT by maximum severity or category. If more than one TEAE of injection site reaction occurs, the event with the worst value (within the individual categories: redness, swelling and pain) will be used.
 
Redness (Scored 0-4)
 
 ○ [0] Subject’s normal skin color, no increased redness ○ [1] Noticeable, but very mild redness ○ [2] Clearly red ○ [3] Bright red ○ [4] Dark with some scar formation 
Swelling (Scored 0-4 after running a finger over injected area)
 
 ○ [0] No bump ○ [1] Barely noticeable ○ [2] Clear bump but very thin ○ [3] Clear bump 1 mm thick ○ [4] Clear bump 2 mm thick or more 
Pain (including burning) (Scored 0-3)
 
 ○ [0] None ○ [1] Mild ○ [2] Moderate ○ [3] Severe 
The duration of TEAE PT for Injection Site Reactions is defined as: Duration of TEAE PT for ISRs (in weeks) = (End date of AE – Start date of AE + 1) / 7.
 
Patients who do not have the PT will not be included in the analysis. If the TEAE has not been reported as ended by the date of completion from the study, or date of early discontinuation, it will be censored as of that date. If a patient has multiple episodes of the same TEAE, the episode with the greatest severity will be used for the duration of event calculation. If a patient has multiple episodes of the same TEAE with the same severity, the episode with the longest duration will be used for the duration of event calculation.
 
The number of TEAE PT for ISRs per 100 active injections is defined as: Number of TEAE PT for ISRs per 100 active injections = $100 \times \text{total number of AEs} / \text{total active injections}.$
	
ISRs by PT within HLT, Number of treatment-emergent ISRs per 100 active injections by PT within HLT
 
Time to onset of initial treatment-emergent ISRs by PT within HLT

--	--	---

	
Time to onset of initial TEAE PT for ISRs is defined as: Time to onset of initial TEAE PT for ISRs (in days) = Start date of first AE – first injection date + 1.
	

Cerebro-cardiovascular Events
	
Cerebro-cardiovascular events will be externally adjudicated by the Central Events Committee (CEC) at the Cleveland Clinic, as outlined in the Manual of Operations. The CEC will adjudicate investigator-reported events selected for adjudication and render an assessment as to whether the event represents a confirmed event (meeting the event definition with all necessary documentation), a non-event (does not meet the event definition and likely represents an alternative or nonevent diagnosis), or lacks sufficient documentation for confirmation of an event. All events selected by investigator for CEC adjudication will be used for the analysis of cerebro-cardiovascular events. The categories of adjudicated events used for the analysis will include the following:
 
 • Cardiovascular 
 ○ Death (Cardiovascular) ○ Myocardial Infarction (MI) ○ Hospitalization for Unstable Angina ○ Hospitalization for Heart Failure ○ Serious Arrhythmia ○ Hospitalization for Hypertension ○ Resuscitated Sudden Death ○ Cardiogenic Shock due to Myocardial Infarction ○ Coronary Revascularization • Neurologic 
 ○ Cerebrovascular Event: Transient Ischemic Attack or Stroke (Hemorrhagic, Ischemic, and Undetermined) • Peripheral Vascular Events 
 ○ Peripheral Arterial Event ○ Peripheral Revascularization 
Events will be analyzed using MedDRA PT nested within the CEC assessment (confirmed event, no event, or insufficient documentation for event determination) and the subcategory. Subtypes of stroke (Hemorrhagic Stroke , Ischemic Stroke, and Undetermined Stroke Type) will be displayed in the analyses nested within Cerebrovascular Event. Subtypes of Serious Arrhythmia (Atrial Arrhythmia, Ventricular Arrhythmia, Heart Block, Other, Unknown) will be displayed nested within Serious Arrhythmia.
	
Blinded Treatment Periods (Fisher’s exact test): TEAE by PT within Subcategory


Major Adverse Cerebro-cardiovascular Events (MACE)
	
MACE (requiring adjudication as defined above) is defined as:
 
 • Vascular death (including cardiovascular and cerebro-vascular causes excluding hemorrhagic deaths outside of the central nervous system) • Non-fatal myocardial infarction • Non-fatal stroke (subcategories: ischemic, hemorrhagic, unknown stroke type) 
Where,
 
 • Vascular death should be captured as an Event on Adjudication - Death eCRF page with Adjudication Death Type = “Cardiovascular.” • Non-fatal myocardial infarction should be captured as an Event on Adjudication - Cardiac Ischemic Event eCRF page with Type of Ischemic Event = “Myocardial Infarction” and the Event is NOT on Adjudication - Death eCRF page. • Non-fatal strokes (ischemic, hemorrhagic) should be captured as an Event on Adjudication - Cerebrovascular Event eCRF page with Stroke Cerebrovascular Event Subtype in one of the following categories: hemorrhagic stroke, ischemic stroke, undetermined stroke type, and the Event is NOT on Adjudication - Death eCRF page. Subcategories of non-fatal stroke (Hemorrhagic Stroke, Ischemic Stroke, and Undetermined Stroke Type) will be displayed nested within non-fatal stroke category. 	
Blinded Treatment Periods (Fisher’s exact test): TEAE by maximum severity by PT within Category


Malignancies
	
Malignancy is defined using PTs from the Malignant or unspecified tumors SMQ as defined in MedDRA (SMQ: 20000091, which includes the sub-SMQs: (1) 20000194 [Malignant tumours], including sub-SMQs of 20000227 [Haematological malignant tumours] and 20000228 [Non-haematological malignant tumours]; (2) 20000195 [Tumours of unspecified malignancy], including sub-SMQs of 20000229 [Haematological tumours of unspecified malignancy] and 20000230 [Non-haematological tumours of unspecified malignancy].
 
Events will be summarized by the following categories:
 
 • Non-Melanoma Skin Cancer (NMSC) 
 ○ Basal Cell Carcinoma, PTs include: 
 ▪ Basal cell carcinoma ▪ Basosquamous carcinoma ▪ Basosquamous carcinoma of skin ○ Squamous Cell Carcinoma, PTs include: 
 ▪ Squamous cell carcinoma of skin ▪ Bowen’s disease ▪ Lip squamous cell carcinoma ▪ Skin squamous cell carcinoma metastatic ▪ Keratoacanthoma • Malignancies excluding NMSC: all PTs in the Malignant or unspecified tumors SMQ excluding the 8 defined NMSC PTs. 	
Blinded Treatment Periods (Fisher’s exact test): TEAE by PT within Category

Depressions	Depression is defined using the PTs from the Depression and suicide/self-injury SMQ as specified in MedDRA (SMQ: 20000035, which includes the sub-SMQs: 20000037 [Suicide/self-injury] and 20000167 [Depression (excl. suicide and self-injury)]).	Blinded Treatment Periods (Fisher’s exact test): TEAE by PT within SMQ or sub-SMQ
Interstitial Lung Disease (ILD)	ILD is defined using the PTs: 
 • Narrow terms in the Interstitial Lung Disease SMQ (20000042) • Additional 6 PTs from Eosinophilic Pneumonia SMQ (20000157): 
 ○ Angiolymphoid hyperplasia with eosinophilia (Narrow) ○ Eosinophilic bronchitis (Narrow) ○ Hypereosinophilic syndrome (Narrow) ○ Löeffler’s syndrome (Narrow) ○ Pulmonary eosinophilia (Narrow) ○ Pulmonary vasculitis (Narrow) 	
Inflammatory Bowel Disease (IBD)	IBD will be identified based on adjudication results. IBD will be also presented according to the following subcategory and MedDRA PTs. IBD Specific Terms (Narrow terms): 
 • Inflammatory Bowel Disease: Inflammatory bowel disease • Crohn’s Disease: Crohn’s disease • Ulcerative Colitis: Acute haemorrhagic ulcerative colitis; Colitis ulcerative; Proctitis ulcerative IBD Non-Specific Terms: The PTs in this category are listed in the compound level safety standard.	Blinded Treatment Periods (Fisher’s exact test): TEAE by PT within Subcategory

Abbreviations: AE = adverse event; eCRF = electronic case report form; FEAE = follow-up emergent adverse event; HLT = high-level term; PT = preferred term; SAE = serious adverse event; SOC = System Organ Class; TB = tuberculosis; TEAE = treatment emergent adverse event.

